7.9 Appropriateness of Measurements

All safety and PK assessments used in this study are standard, ie, widely used and generally recognized as reliable, accurate, and relevant.

8 QUALITY CONTROL AND QUALITY ASSURANCE

According to the GCP guidelines, the sponsor is responsible for implementing and maintaining quality assurance and quality control systems with written standard operating procedures (SOPs).

Quality control will be applied to each stage of data handling.

The following steps will be taken to ensure the accuracy, consistency, completeness, and reliability of the data:

- Investigator meeting(s)
- Certified local laboratories for laboratory measurements and 12-lead ECGs
- Study center initiation visit
- Early study center visits post-enrollment
- Routine study center monitoring
- Ongoing study center communication and training
- Data management quality control checks
- Continuous data acquisition and cleaning
- Internal review of data
- Quality control check of the final clinical study report
- Certified independent radiology review (Phase 2 Section)
- Certified ECT result central reading (for patients who contribute to PK sample collection in Phase 2 portion)

In addition, the sponsor and/or the contract research organization clinical quality assurance department may conduct periodic audits of the study processes, including, but not limited to the study center, central laboratories, vendors, clinical database, and the final clinical study report. When audits are conducted, access must be authorized for all study-related documents including medical history and concomitant medication documentation to authorized Sponsor's representatives and regulatory authorities.

8.1 Monitoring

In accordance with applicable regulations, GCP, and sponsor procedures, the sponsor and/or contract research organization monitors will contact the study center prior to the patient enrollment to review the protocol and data collection procedures with the study center personnel. In addition, the medical monitor will periodically contact the study center, including conducting on-site visits. The extent, nature and frequency of on-site visits will be based on such considerations as the study objective and/or endpoints, the purpose of the study, study design complexity, and enrollment rate.

During these contacts, the medical monitor will:

- Check the progress of the study
- Review study data collected
- Conduct source document verification
- Identify any issues and address their resolution

This will be done in order to verify that:

- Data are authentic, accurate, and complete
- Safety and rights of patients are being protected
- Study is conducted in accordance with the currently approved protocol (and any amendments), GCP, and all applicable regulatory requirements

The investigator agrees to allow the monitor direct access to all relevant documents and to allocate his/her time and the time of his/her personnel to the medical monitor to discuss findings and any relevant issues.

At study closure, monitors will also conduct all activities described in Section 12.1.

8.2 Data Management/Coding

Data generated within this clinical study will be handled according to the relevant SOPs of the data management and biostatistics departments.

An electronic data capture (EDC) system will be used for this study, meaning that all eCRF data will be entered in electronic forms at the study center. Data collection will be completed by authorized study center personnel designated by the investigator. Appropriate training and security measures will be completed with the investigator and all authorized study center personnel prior to the study being initiated and any data being entered into the system for any patients.

The eCRFs should always reflect the latest observations on the patients participating in the study. Therefore, the eCRFs are to be completed as soon as possible during or after the patient's visit. To avoid inter-observer variability, every effort should be made to ensure that the same individual who made the initial baseline determinations completes all safety evaluations. The investigator must verify that all data entries in the eCRFs are accurate and correct. If some assessments are not done, or if certain information is not available or not applicable or unknown, the investigator should indicate this in the eCRF. The investigator will be required to electronically sign off on the clinical data.

The monitor will review the eCRFs and evaluate them for completeness and consistency. The eCRF will be compared with the source documents to ensure that there are no discrepancies between critical data. All entries, corrections, and alterations are to be made by the responsible investigator or his/her designee. The monitor cannot enter data in the eCRFs. Once clinical data of the eCRF have been submitted to the central server, corrections to the data fields will be audit trailed, meaning that

the reason for change, the name of the person who performed the change, together with time and date will be logged. Roles and rights of the study center personnel responsible for entering the clinical data into the eCRF will be determined in advance. If additional corrections are needed, the responsible monitor or data manager will raise a query in the EDC application. The appropriate study center personnel will answer queries sent to the investigator.

The eCRF is essentially considered a data entry form and should not constitute the original (or source) medical records unless otherwise specified. Source documents are all documents used by the investigator or hospital that relate to the patient's medical history, that verify the existence of the patient, the inclusion and exclusion criteria and all records covering the patient's participation in the study. They include laboratory notes, ECG results, memoranda, pharmacy dispensing records, patient files, etc.

The investigator is responsible for maintaining source documents. These will be made available for inspection by the study monitor at each monitoring visit. The investigator must submit a completed eCRF for each patient who receives pamiparib, regardless of the duration. All supportive documentation submitted with the eCRF, such as laboratory or hospital records, should be clearly identified with the study and patient number. Any personal information, including patient name, should be removed or rendered illegible to preserve individual confidentiality.

Electronic CRF records will be automatically appended with the identification of the user, by means of their unique user ID. Specified records will be electronically signed by the investigator to document his/her review of the data and acknowledgement that the data are accurate. This will be facilitated by means of the investigator's unique user ID and password; date and time stamps will be added automatically at the time of the electronic signature. If an entry on an eCRF requires change, the correction should be made in accordance with the relevant software procedures. All changes will be fully recorded in a protected audit trail, and a reason for the change will be required.

AEs will be coded using the Medical Dictionary for Regulatory Activities (MedDRA), version 18.1 or higher, and graded using the current version of NCI-CTCAE. Concomitant medications will be coded using the World Health Organization Drug Dictionary. Concomitant diseases/medical history will be coded using the MedDRA, version 18.1 or higher.

8.3 Quality Assurance Audit

To ensure compliance with GCP and all applicable regulatory requirements, the sponsor may conduct a quality assurance audit. Regulatory agencies may also conduct a regulatory inspection of this study. Such audits/inspections can occur at any time during or after completion of the study. If an audit or inspection occurs, the investigator and institution agree to allow the auditor/inspector direct access to all relevant documents and to allocate his/her time and the time of his/her personnel to the auditor/inspector to discuss any relevant issues found.

9 SAFETY MONITORING AND REPORTING

The investigator is responsible for the monitoring and documentation of events that meet the criteria and definition of an AE or SAE as provided in this protocol.

9.1 Adverse Events

9.1.1 Definition and Reporting of an Adverse Event

An AE is defined as any unfavorable and unintended sign (including an abnormal laboratory finding), symptom, or disease (new or exacerbated) temporally associated with the use of a study drug, whether considered related to study drug or not.

Examples of an AE include:

- Worsening of a chronic or intermittent pre-existing condition including an increase in severity, frequency, duration, and/or has an association with a significantly worse outcome
- New conditions detected or diagnosed after study drug administration even though it may have been present before the start of the study
- Signs, symptoms, or the clinical sequelae of a suspected interaction
- Signs, symptoms, or the clinical sequelae of a suspected overdose of either study drug or a concurrent medication (overdose per se should not be reported as an AE or SAE)

When an AE or SAE occurs, it is the responsibility of the investigator to review all documentation (eg, hospital progress notes, laboratory results and diagnostics reports) relative to the AE or SAE. The investigator will then record all relevant information regarding an AE or SAE in the eCRF. However, there may be instances when copies of medical records for certain cases are requested by the Sponsor. In this instance, all patient identifiers will be blinded on the copies of the medical records prior to submission to the sponsor.

9.1.2 Assessment of Severity

The investigator will make an assessment of severity for each AE and SAE reported during the study. AEs and SAEs should be assessed and graded based upon the NCI-CTCAE, version 4.03.

Toxicities that are not specified in the NCI-CTCAE will be defined as follows:

- Grade 1: Mild; asymptomatic or mild symptoms; clinical or diagnostic observations only; intervention not indicated
- Grade 2: Moderate; minimal, local or noninvasive intervention indicated; limiting ageappropriate instrumental activities of daily living
- Grade 3: Severe or medically significant but not immediately life-threatening; hospitalization or prolongation of hospitalization indicated; disabling; limiting self-care activities of daily living
- Grade 4: Life-threatening consequences; urgent intervention indicated

• Grade 5: Death related to AE

NOTE: The terms "severe" and "serious" are not synonymous. Severity is a measure of intensity (for example, grade of a specific AE, mild [Grade 1], moderate [Grade 2], severe [Grade 3], or life-threatening [Grade 4]), whereas seriousness is classified by the criteria based on the regulatory definitions. Seriousness serves as the guide for defining regulatory reporting obligations from the Sponsor to applicable regulatory authorities as described in Section 9.2.

9.1.3 Assessment of Causality

The investigator is obligated to assess the relationship between the study drug and the occurrence of each AE or SAE. The investigator will use clinical judgment to determine the relationship. Alternative causes, such as natural history of the underlying diseases, concomitant therapy, and other risk factors, and the temporal relationship of the AE or SAE to the study drug will be considered and investigated. The investigator will also consult the IB and/or product information for marketed products in the determination of his/her assessment.

There may be situations when an SAE has occurred and the investigator has minimal information to include in the initial report to the Sponsor. However, it is very important that the investigator always makes assessment of causality for every SAE prior to transmission of the SAE report/eCRF to the sponsor since the causality assessment is one of the criteria used when determining regulatory reporting requirements. The investigator may change his/her opinion of causality in light of follow-up information, amending the SAE report/eCRF accordingly.

Investigators must also systematically assess the causal relationship of AEs to study drug (including any other non-study drugs, radiation therapy, etc.) using the following definitions:

- Definitely related: There is clear evidence to suggest a causal relationship to the study drug, and there is reasonable temporal relationship; the occurrence of AE is definitely attributed to the pharmacological effect of study treatment.
- Probably related: There is a reasonable temporal relationship to suggest a causal relationship to the study drug; the occurrence of AE could not be explained by the patient's medical history, concurrent medical condition, or other the patient's signs or symptoms.
- Possibly related: There is some evidence to suggest a causal relationship to the study drug (eg, the AE occurred within a reasonable time after administration of the study drug). However, the influence of other factors may have contributed to the AE (such as the patient's clinical condition, other concomitant AEs).
- Unlikely related: There is little evidence to suggest there is a causal relationship to the study drug. There is another reasonable explanation for the AE such as disease or other drugs.
- Unrelated: An AE will be considered "not related" to the use of study drug if any of the following criteria are met:

- An unreasonable temporal relationship between administration of the drug and the onset on the AE (eg, the AE occurred either before, or too long after administration of the drug for it to be considered drug-related);
- A causal relationship between study drug and the AE is biologically implausible (eg, death as a passenger in an automobile accident);
- A clearly more likely alternative explanation for the AE is present (eg, typical adverse reaction to a concomitant drug and/or typical disease-related AE).

The causality for cases assessed with 5-point scale will be mapped to 2-point scale during aggregate safety data analysis according to the BeiGene latest mapping rule.

9.1.4 Follow-Up of Adverse Events

After the initial AE or SAE report, the investigator is required to proactively follow each patient and provide further information to the sponsor on the patient's condition.

All AEs and SAEs documented at a previous visit/contact and designated as ongoing will be reviewed at subsequent visits/contacts.

All AEs and SAEs will be followed until resolution, the condition stabilizes or is considered chronic, the AE or SAE is otherwise explained, the patient is lost to follow-up or the patient withdraws consent. The investigator will ensure that follow-up includes any supplemental investigations as may be indicated to elucidate the nature and/or causality of the AE or SAE. This may include additional laboratory tests or investigations, histopathological examinations, or consultation with other health care professionals.

The sponsor may request that the investigator perform or arrange for the conduct of supplemental measurements and/or evaluations to elucidate as fully as possible the nature and/or causality of the AE or SAE. The investigator is obligated to assist. If a patient dies during participation in the study or during a recognized follow-up period, the sponsor will be provided with a copy of any post-mortem findings, including histopathology.

New or updated information should be reported to the sponsor according to the SAE instructions provided by the sponsor within the time frames outlined in Section 9.6.1.

9.1.5 Laboratory Test Abnormalities

Abnormal laboratory findings (e.g., chemistry, hematology, coagulation [only for Phase 1 portion]) or other abnormal assessments (ECGs, X-rays, vital signs) that are judged by the investigator as clinically significant will be recorded as adverse events or serious adverse events. This includes clinically significant abnormal laboratory findings or other abnormal assessments that are present at baseline and significantly worsen during the study. The definition of clinically significant is left to the judgment of the investigator; in general, these are the abnormalities that are associated with clinical signs or symptoms, require active medical intervention, or lead to dose interruption or

discontinuation, or require close observation, or more frequent follow-up assessments, or further diagnostic investigation.

9.2 Definition of a Serious Adverse Event

An SAE is any untoward medical occurrence that, at any dose:

- Results in death
- Is life-threatening

NOTE: The term "life-threatening" in the definition of "serious" refers to an AE in which the patient was at risk of death at the time of the AE. It does not refer to an AE, which hypothetically might have caused death, if it were more severe.

• Requires hospitalization or prolongation of existing hospitalization

NOTE: In general, hospitalization signifies that the patient was admitted (usually involving at least an overnight stay) to the hospital or emergency ward for observation and/or treatment that would not have been appropriate in the physician's office or outpatient setting.

• Results in disability/incapacity

NOTE: The term disability means a substantial disruption of a person's ability to conduct normal life functions. This definition is not intended to include experiences of relatively minor medical significance, such as uncomplicated headache, nausea, vomiting, diarrhea, influenza, and accidental trauma (eg, sprained ankle), which may interfere or prevent everyday life functions, but do not constitute a substantial disruption.

- Is a congenital anomaly/birth defect
- Is considered a significant medical AE by the investigator based on medical judgement (eg, may jeopardize the patient or may require medical/surgical intervention to prevent one of the outcomes listed above)

The following are NOT considered SAEs:

- Hospitalization for elective treatment of a pre-existing condition that did not worsen from baseline
- Hospitalization for social/convenience considerations
- Scheduled therapy for the target disease of the study, including admissions for transfusion support or convenience

9.3 Suspected Unexpected Serious Adverse Reaction

A suspected unexpected serious adverse reaction (SUSAR) is a serious adverse reaction that is both unexpected (ie, not present in the product's Reference Safety Information [RSI] in the IB) and meets

the definition of a serious adverse drug reaction (SADR), the specificity or severity of which is not consistent with those noted in the IB.

9.4 Timing, Frequency, and Method of Capturing Adverse Events and Serious Adverse Events

9.4.1 Adverse Event Reporting Period

After main informed consent has been signed at screening but prior to study treatment, only SAEs should be reported.

After initiation of study treatment, all AEs and SAEs, regardless of relationship to study treatment, will be reported until 30 days after last study treatment or initiation of new anti-cancer therapy, whichever occurs first. After this period, the investigator should report any SAEs including death that are believed to be related to prior study treatment.

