4.1.2.1 Safety, Tolerability and Efficacy

Phase 2 portion will investigate efficacy in patients with selected tumor types and further evaluate safety and tolerability of pamiparib at 60 mg BID.

Patients will be monitored for safety, tolerability, and efficacy throughout the study. Radiological assessment of tumor response status should be performed approximately once every 6 weeks \pm 7 days for the first 18 weeks, thereafter once every 9 weeks \pm 7 days for the remaining period in the first year, and then once every 12 weeks \pm 7 days starting with the second year. For patients with first a response as complete response (CR) or partial response (PR), a response confirmation will need to be performed during the following 4-6 weeks, then patients will keep original tumor assessments schedule per protocol.

Tumor response will be assessed by IRR and investigators separately based on RECIST, version 1.1.

Patients will continue treatment until occurrence of unacceptable toxicities, disease progression, withdrawal of consent, investigator discretion, or delay of treatment due to unresolved toxicities for more than 21 days. Dose interruption due to investigational drug-related anemia could be on hold for up to 56 days consecutively.

Assessments ⁷	Pre- screening ¹	Screening ¹	Cycle 1 (21 days)	Cycle 2 (21 days)	Cycle 3 and subsequent Cycles (every 21 days for one cycle)	Unscheduled Visit ²	EOT Visit ³	Safety Follow-up ⁴	Survival Follow- up ⁵
Day of Study	Before screening	D -21 to -1	D1	D22	D43~	Varies	Within 5 days after	30 ± 5 days after last	Every 12 weeks
Allowed time window				±3 days	±3 days		last dose	dose	±7 days
Informed consent	Х	Х							
Baseline demographics		Х							
Medical history/treatment history ⁶		х							
Concurrent medications		Х	Х	Х	Х	Х	Х	Х	
Physical examination ⁸		Х	Х	Х	Х	Х	Х		
Vital signs		X	Х	Х	Х	Х	Х		
Height		X							
Weight		X				Х	Х		
ECOG performance status		X	Х	Х	X	Х	Х		
Hematology ⁹		-7 to -1 X	Х	X	x	Х	Х		
Clinical chemistry ⁹		-7 to -1 X	Х	Х	X	Х	Х		

1.0

Assessments ⁷	Pre- screening ¹	Screening ¹	Cycle 1 (21 days)	Cycle 2 (21 days)	Cycle 3 and subsequent Cycles (every 21 days for one cycle)	Unscheduled Visit ²	EOT Visit ³	Safety Follow-up⁴	Survival Follow- up ⁵
Day of Study	Before screening	D -21 to -1	D1	D22	D43~	Varies	Within 5 days after	30 ± 5 days after last	Every 12 weeks
Allowed time window				±3 days	±3 days		last dose	dose	±7 days

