3. EOT visit should be conducted at the earliest day as possible within 5 days of the last dose of pamiparib, if possible. If discontinuation is due to unresolved toxicities for more than 21 days (56 days for anemia), EOT visit should be conducted at the earliest day as possible within 5 days after permanent discontinuation is determined. The CT/MRI does not have to be repeated if it was performed at a prior response evaluation that documented progressive disease. CA-125 and ECG do not have to be repeated if it was performed within 14 days of the EOT visit, For the other required assessment, if they were performed within 4 days of the EOT visit, they do not need to be repeated on EOT visit

- 4. Approximately 30 days after the last day of pamiparib, a safety follow-up visit will occur with the outlined safety assessments. If a new anti-cancer therapy is initiated before this safety follow-up, a safety follow-up should be scheduled as soon as possible ideally before other anti-cancer treatment starts. For patients who do not want to or cannot return to the clinic for the safety follow-up, the patient should be contacted by phone for a review of AEs. If discontinuation is due to unresolved toxicities for more than 21 days, safety follow-up could be scheduled 30 ± 5 days after the last dose of treatment. If discontinuation is due to unresolved toxicities for more than 56 days for anemia, safety follow-up could be scheduled at the earliest day possible within 5 days after permanent discontinuation is determined
- 5. Patients will be followed for survival via phone contact approximately every 12 weeks \pm 7 days or as otherwise directed by the sponsor
- 6. Date of and response to last platinum treatment must be documented (unless no platinum treatment has been received). Patients are defined as platinum-sensitive if disease progression by RECIST or CA-125 criteria had occurred ≥ 6 months after their last dose of platinum treatment while platinum-resistant is defined as disease progression that occurred < 6 months after the last dose of platinum
- 7. All assessments, unless stated otherwise, must be performed before investigational product administration in each cycle
- Full physical examination includes the following items: 1) general appearance; 2) head, eyes, ears, nose and throat; 3) neck; 4) heart; 5) chest (including lungs); 6) abdomen;

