4.1.3 Follow-up for Toxicities

When treatment is interrupted or permanently discontinued due to an AE or abnormal laboratory value, the patient must be followed at a frequency as medically indicated until resolution or stabilization of the event, whichever comes first. All patients will be followed for AEs and SAEs for at least 30 days following the last dose of pamiparib.

For prolonged hematological toxicities, treatment should be interrupted and blood counts should be monitored weekly until recovery. If the levels have not recovered to NCI-CTCAE \leq Grade 1 or baseline after 8 weeks, the patient should be referred to a hematologist for further investigations, including bone marrow analysis and blood sample for cytogenetics. If MDS/AML is diagnosed, treatment of pamiparib must be permanently discontinued, and the event should be reported as an SAE regardless of causality.

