7.6 Follow-up Assessments

Approximately 30 days after the last administration of pamiparib, all patients should return for a safety follow-up evaluation. Assessments to be performed are presented in Table 5 for Phase 1, and Table 7 for Phase 2.

Patients who are discontinued from the study due to an unacceptable drug-related AE will be followed until the resolution of the AE to \leq Grade 1 or stabilization or non-laboratory toxicities.

Patients with treatment terminated prior to documentation of PD shall be subjected to CT/MRI/CA-125 disease assessment according to the previous visit assessment scheme, until 1) commencement of new treatment, 2) disease progression, 3) death or 4) termination of the study. Following completion of the treatment and safety follow-up periods, all patients will be followed for survival status in the survival follow-up period specified by the protocol (only for Phase 2). Patients will have their survival status assessed approximately every 3 months by either a telephone or in-person contact until study completion or termination by the sponsor. No other data (eg, subsequent therapies, performance status, etc.) beyond survival will be collected during these calls/visits.

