#### 6.3.5 Prior and Concomitant Medications

Prior and concomitant medications will be coded using WHO DD and will be further classified to the appropriate Anatomical Therapeutic Chemical (ATC) code.

The number (percentage) of patients reporting prior and concomitant medications will be summarized by ATC medication class and WHO DD preferred term by phase in the safety analysis set. Prior medications are defined as medications that stopped before the first dose date. Concomitant medications will be defined as medications that (1) started before the first dose of study drug and were continuing at the time of the first dose of study drug, or (2) started on or after the date of the first dose of study drug up to 30 days after the patient's last dose or initiation of a new anticancer therapy. A listing of prior and concomitant medications will be provided.

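### For a patient who stops for good after an anaemia hold of more than 56 days, the adverse-event and concomitant-medication windows close at day 30, before the moved safety follow-up visit at about day 56 to 61

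*Protocol*

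**What the plan says.** **Windows tied to the last dose**

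- *AE reporting (Protocol 9.4.1).* After treatment starts, AEs and SAEs of any causality "will be reported until 30 days after last study treatment or initiation of new anti-cancer therapy, whichever occurs first". Later reports are limited: "After this period, the investigator should report any SAEs including death that are believed to be related to prior study treatment".
- *Concomitant medications.* Protocol 6.1 sets a recording window ending 30 days after the last dose, although the same section also asks for everything taken during the study. For analysis, Protocol 10.2.5 stops at 30 days after the last dose, and SAP 6.3.5 counts medications started "up to 30 days after the patient's last dose or initiation of a new anticancer therapy".
- *Treatment-emergent AEs (Protocol 10.4.2, SAP 6.5.3).* The cut-off is 30 days after discontinuation of study drug, and that date is not defined. All AEs are listed, but only treatment-emergent ones enter the summary tables.

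**Rules that run longer**

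- *Hold length (Protocol 4.1.2.1).* "Dose interruption due to investigational drug-related anemia could be on hold for up to 56 days consecutively". For other unresolved toxicities the limit is 21 days.
- *Moved visit (Table 7 footnote 4).* When anaemia stays unresolved beyond 56 days, "safety follow-up could be scheduled at the earliest day possible within 5 days after permanent discontinuation is determined". Table 7 schedules both AE and concurrent-medication collection at that visit.
- *MDS/AML (Protocol 4.1.3).* Haematology referral follows 8 weeks without recovery. If MDS/AML is diagnosed, "the event should be reported as an SAE regardless of causality". No time limit is given.
- *Survival follow-up (Protocol 7.6).* No data "beyond survival will be collected during these calls/visits".

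**The concern.** The 30-day windows suit a patient whose last dose and stopping decision fall close together. They do not suit a patient whose drug is held for anaemia, who does not recover within 56 days, and who is then taken off treatment. Her last dose is fixed in retrospect at the start of the hold. By the time the decision is made and the safety visit takes place, the reporting period and the medication analysis window have already closed. A site is told to collect AEs and medications at a visit whose content the other sections place out of range.

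Safety and tolerability is a Phase 2 secondary objective, and the protocol singles out haematological toxicity and MDS/AML. SAP Appendix 10.2 compares haematological safety before and after amendment 5.0, including the number of patients given erythropoietin or red cell transfusion (C4). These rules decide what is counted for the patients with the longest unrecovered anaemia.

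**Working it through.** The plan states no figure on this point, so there is none to reproduce. The check is date arithmetic with day 0 as the last dose taken.

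**Inputs.** AE and medication windows: 30 days (Protocol 9.4.1, 6.1, 10.2.5; SAP 6.3.5). Maximum anaemia hold: 56 days (Protocol 4.1.2.1). Referral: 8 weeks, and 8 × 7 = 56 days (Protocol 4.1.3). Safety visit: up to 5 days after the decision (Table 7 footnote 4). Limit for other toxicities: 21 days (Protocol 4.1.2.1).

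**Patient who never restarts after a full anaemia hold**

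| Step | Arithmetic | Result |
|---|---|---|
| Windows close | given | day 30 |
| Hold limit and referral point | 8 × 7 | day 56 |
| Window closes before the hold limit by | 56 − 30 | 26 days |
| Latest moved safety visit | 56 + 5 | about day 61 |
| Window closes before that visit by up to | 61 − 30 | 31 days |
| Treatment-emergent cut-off if discontinuation means last dose | 0 + 30 | day 30 |
| Treatment-emergent cut-off if it means the decision | 56 + 30 | about day 86 |

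**Patient who restarts.** The last dose is later and the hold lies inside the treatment period, so the gap is 0 days. Whether treatment given during the same length of hold is counted therefore depends on whether the patient resumed.

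**Other toxicities.** 21 + 5 = day 26 for the end-of-treatment visit, which is inside day 30. The mismatch is specific to anaemia.

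**What happens to each kind of data from day 31 to the visit**

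1. *New AEs.* Non-serious events, and serious ones judged unrelated, need not be reported under Protocol 9.4.1. Related SAEs remain reportable.
2. *Medications.* Even if collected at the moved visit, erythropoietin or a transfusion first started after day 30 is not concomitant under Protocol 10.2.5 or SAP 6.3.5. It drops out of the medication tables and, since C4 states no window of its own, out of the C4 counts. The SAE route does not recover it, because Protocol 9.2 does not count admissions for transfusion support as SAEs.
3. *Treatment-emergent tables.* The same new event is in or out according to which date is taken as discontinuation.
4. *MDS/AML judged unrelated.* Protocol 4.1.3 requires a report and 9.4.1 does not. A reported late case would be listed but could be absent from the summary tables. MDS and AML are also not among the haematological preferred terms in Appendix 10.2 C2.

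**The case against.** Several rules limit the loss, and they stand.

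- The anaemia began before the hold, so it is treatment-emergent, and it is followed to resolution or stabilisation (Protocol 4.1.3, 9.1.4).
- Protocol 4.1.3 sets a floor rather than a ceiling: "All patients will be followed for AEs and SAEs for at least 30 days following the last dose of pamiparib".
- During the hold nobody knows that the last dose has been taken, so sites will probably go on recording. Protocol 6.1 also asks for all medications taken during the study, and 4.2.3.1 wants the investigator told of any medication until discharge from the study. The recording rule is therefore inconsistent rather than plainly closed at day 30. The analysis rule is not rescued by this, because it counts from the last dose whatever was collected.
- C4 counts patients, not transfusions. A patient is lost from it only if her first erythropoietin or transfusion comes after day 30.
- MDS/AML must be reported under 4.1.3. Because the 56-day hold applies to drug-related anaemia, a marrow disorder emerging from it may well be judged related and so be reportable under 9.4.1 too.

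A reader might infer that late toxicity in these patients falls outside the safety data altogether, or that MDS/AML incidence will be understated. The rules above do not support that. Nor does it help to apply the MDS/AML rates quoted in the protocol (below 1% for PARP inhibitors, 1.4% with niraparib) to 100 patients. That gives the chance of any case, not of a case that is late and missed. Protocol 1.4.3 also reports no case in any pamiparib study to date.

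**Conclusion.** The windows and the moved visit do not fit together for one defined group: Phase 2 patients who stop permanently after an anaemia hold of more than 56 days. For them the windows close 26 days before the 56-day limit and up to 31 days before the visit that collects the data. This assumes that the decision comes at about day 56 and that the visit is scheduled as footnote 4 allows.

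Three kinds of data are lost or uncertain: new non-serious or unrelated AEs, first use of erythropoietin or transfusion, and the treatment-emergent status of late events. Separately, Protocol 4.1.3 and 9.4.1 conflict on a late MDS/AML case judged unrelated. Because survival contacts collect survival only, such cases depend on unprompted reporting.

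The documents give no frequency of such holds, so neither the number of patients nor the effect on any reported rate can be computed. The point still merits correction: followed as written, the rules discard data that the protocol schedules a visit to collect.

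**What to change.** 1. End the AE-reporting, treatment-emergent and concomitant-medication windows at the later of 30 days after the last dose and the safety follow-up visit. Keep the new-anticancer-therapy cut-off where it is now stated. Apply this in the synopsis, Protocol 6.1, 9.4.1, 10.2.5 and 10.4.2, and SAP 6.3.5 and 6.5.3. The treatment-emergent definition then no longer needs an undefined discontinuation date.
2. In Protocol 9.4.1, exempt MDS/AML from the limit to related SAEs, so that it agrees with 4.1.3. In the SAP, tabulate all reported MDS/AML cases whatever their onset.

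Tying the end to the visit is better than running 30 days from the decision. That alternative reaches about day 86, which is 86 − 61 = 25 days past the last scheduled safety collection.

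The cost is wording, with no extra visits. A few more late events, some disease-related, will enter the tables. Patients on the ordinary schedule of 30 ± 5 days may gain up to 5 days of window. A question on MDS/AML at the survival contact is optional and would also need a change to Protocol 7.6. No change to the hold length or to the timing of the haematology work-up is proposed.
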